# Hypothesis 2. Participants with MCI randomized to Games will show more improvement in functional outcomes as compared to Crosswords.

There were two functional outcomes: UPSA and FAQ.

Main functional outcome: UPSA total score measured at baseline, 32 weeks and 78 weeks. Additional functional outcome: FAQ total score measured at baseline, 12 weeks, 20 weeks, 32 weeks, 52 weeks and 78 weeks.

Hypothesis 3. The proportion of participants converting to dementia will be lower in the Games group as compared to Crosswords.

Outcome: Binary indicator of transitioning from MCI to dementia at 78 weeks.

Hypothesis 4: Alzheimer's disease risk variables (apolipoprotein E e4 genotype, baseline hippocampal volume, baseline UPSIT score) will moderate the relationship between treatment group and change in ADAS-Cog11, the primary outcome.

Exploratory Hypothesis: Participants with MCI randomized to Games will show less decline in brain MRI outcomes as compared to Crosswords.

Outcomes: change in hippocampal volume from baseline to 78 weeks; change in cortical thickness from baseline to 78 weeks.

# 4. Sample Size Calculation.

The sample size was calculated based on the primary outcome: change in ADASCog11 from baseline to end-point week 78. Power analysis used the RMASS program for longitudinal studies. A sample size of 100 participants was projected to detect an effect size of d=.58 with 80% power at 5% level of significance, assuming dropout uniformly distributed over time to reach 20% by 78 weeks. The projected sample size increased to 110 to balance site demographics based on DSMB recommendation but ended at 107 in March 2020 because of pandemic restrictions.

### 5. Statistical analysis

The analyses were conducted on the Intent-to-treat (ITT) sample, i.e., all randomized participants according to the treatment that they were assigned. Missing data on outcome variables were dealt with by using (longitudinal) linear mixed effects models which do not require complete measurements under the "missing at random" assumption. All hypotheses were tested at level of significance of 5%. There was no adjustment for multiple statistical comparisons in this pilot trial. All analyses were conducted using SAS 9.4.

Before testing the hypotheses, we first examined patients' baseline characteristics to make sure covariates were balanced between the two treatment arms. Nonparametric Wilcoxon's rank sum test was used for continuous and ordinal variables and Fisher's exact test was used for categorical variables.

Linear mixed effects models were used to evaluate the efficacy of Games as compared to Crosswords on cognitive and functional outcomes (**Hypotheses 1 and 2**). Specifically, for each outcome measure, we considered the following model

$$\Delta Y_{it} = \beta_0 + \beta_1 * Group_i + \alpha * Time_{it} + \gamma * Group_i * Time_{it} + \delta Y_{i0} + b_i + \epsilon_{it}, \tag{1}$$

where  $\Delta Y_{it}$  is change of the outcome measure (baseline minus t weeks) for participant i at timepoint t,  $Group_i$  is the treatment group indicator for participant i (1= Games and 0=crosswords),  $Time_{it}$  is the visit time point (treated as a categorical variable),  $Y_{i0}$  is baseline value of the outcome measure for participant i,  $b_i$  is a participant-specific random intercept, and  $\epsilon_{it}$  is the unexplained residual error term. ( $\beta_0$ ,  $\beta_1$ ,  $\alpha$ ,  $\gamma$ ,  $\delta$ ) are fixed effects parameters. SAS PROC MIXED procedure was used to estimate the parameters using REML and random

intercept model. The efficacy of Games versus Crosswords at each time point was tested by forming contrasts of the fitted model. This model was then further adjusted for the three stratification variables (site, age group and MCI type).

We also conducted stratified analysis for each stratification factor separately. For example, for MCI type, we modify model (1) to incorporate interaction with MCI type, namely,

$$\Delta Y_{it} = \beta_0 + \beta_1 * Group_i + \alpha * Time_{it} + \gamma * Group_i * Time_{it} + \delta Y_{i0}$$

$$+ (\beta_2 + \beta_3 * Group_i + \alpha_1 * Time_{it} + \gamma_1 * Group_i * Time_{it} + \delta_1 Y_{i0})$$

$$* MCItype_i + b_i + \epsilon_{it},$$
(2)

The efficacy of Games versus Crosswords for early MCI and late MCI at each time point was tested by forming contrasts of the fitted model.

For **Hypothesis 3**, Fisher's exact test was used to test the association between the binary outcome of dementia and treatment group. Since the number of participants transitioning to dementia was very small, we didn't further adjust for covariates.

For **Hypothesis 4**, linear mixed effects models were used to examine the moderator effect of each Alzheimer's disease risk variable. The model is similar to (2) with MCI type replaced by the Alzheimer's disease variable. The moderator effect was examined by testing the moderator by treatment interaction at each time point.

For the **exploratory hypothesis**, linear regression model was used to compare the effect of treatment on change in MRI outcome (baseline minus 78 weeks), adjusting for baseline values of the MRI measure. The model was then further adjusted for the three stratification variables. Parameters were estimated using SAS PROC GENMOD procedure with normal distribution and identity link.

For safety and compliance, we examined adverse events and number of completed sessions. For each type of adverse event, number and proportion of participants who experienced the adverse event was reported and compared by treatment arms using Fisher's exact test. Number of completed sessions was compared by treatment groups, and separately by site, using Wilcoxon's rank sum test. The proportion that had treatment interruption due to Covid-19 was reported and compared by treatment groups using Fisher's exact test.

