All infection control guidelines and procedures stipulated at the top of the "Study Visit Procedures" (prior to description of screening visit) and Baseline/Week 0 sections of the PSF will be followed.

A MRI scan, GDS, CIRS-G, FAQ, MMSE, ADAS-Cog11, neuropsychological testing battery, Digit Symbol Substitution Test, Expectancy Scale (Participant & Informant), UPSA, UPSIT, History of Game Use Questionnaire, and User Engagement Scale, **Pittsburgh Sleep Quality Index (PSQI) and Epworth Sleepiness Scale (ESS)** will be completed. The study physician or neuropsychologist will complete the

Protocol Summary Form

Diagnosis Form and Contributing Features to MCI Form. The participant will also complete the NCPT online cognitive test and cognitive training or control training booster session.

Time Line. The sample (n=100) will be recruited over 3.5 years (includes 2 months start-up time to set up CCT platform and review MRI phantom scans). Treatment duration is 1.5 years. Total project duration is 5 years. Data entry/cleaning will be done throughout the project. Analyses and publications from baseline data will begin during the study and analyses of trial results will be done at the end of the trial.

Study duration: Total study duration may exceed 78 weeks for those participants encountering delays to in person assessments and/or procedures related to COVID-19 specific pauses to research protocol implementation. Any pause to research activity, specific to COVID-19, has, or may, be put into place as part of institutional risk reduction initiative(s). From a research perspective, this delay will be addressed by evaluating time in study as a covariate in statistical analyses of outcome measures, as appropriate.

Blindness of raters. The raters completing the outcome measures will be blind to which type of cognitive training (active or comparison) the patient is performing. Participants will be instructed not to discuss their online training with any tester or rater in order to maintain blindness.

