#### 1. Introduction.

The aim of the study was to evaluate the efficacy of computerized cognitive training (suite of videogames, denoted as "Games") as compared to computerized crossword puzzle training (denoted as "Crosswords") in the two-site, 78-week, COG-IT randomized clinical trial for study participants with mild cognitive impairment (MCI). This statistical analysis plan provides more detailed descriptions of the statistical analyses reported in the paper.

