### 3. Hypotheses and Outcome Measures.

Hypothesis 1. Participants with MCI randomized to Games will show more improvement in cognitive outcomes as compared to Crosswords.

Primary outcome: ADAS-Cog 11 total score measured at baseline, 12 weeks, 52 weeks and 78 weeks.

Secondary outcome: Neuropsychological Testing Composite z-score measured at baseline, 12 weeks, 52 weeks and 78 weeks. Another secondary outcome, NCPT online cognitive performance test (measured at baseline and 78 weeks), was not analyzed because only 54 of 107 participants provided week 78 data due to software discontinuation.

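### The random-intercept model assumes the same spread of change at every visit; if the spread differs, the week-78 standard error is wrong, and the SAP states no check

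*SAP*

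**What the plan says.** SAP section 5 defines model (1) for the change from baseline in each outcome. Its fixed effects are group, visit, their interaction and the baseline value. The only random term "is a participant-specific random intercept", and there is one residual term. On fitting, it says "SAS PROC MIXED procedure was used to estimate the parameters using REML and random" intercept model. On testing: "The efficacy of Games versus Crosswords at each time point was tested by forming contrasts of the fitted model".

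Section 3 gives "Primary outcome: ADAS-Cog 11 total score measured at baseline, 12 weeks, 52 weeks and 78 weeks", so three post-baseline visits enter the model. Section 4 fixes the visit that matters most: "The sample size was calculated based on the primary outcome: change in ADASCog11 from baseline to end-point week 78".

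The SAP does not mention a REPEATED structure, an unstructured or heterogeneous covariance, a random slope, robust standard errors, a degrees-of-freedom method or a covariance check. The protocol's only sensitivity analysis (Study Procedures, paragraph on intent to treat and missing data) concerns non-ignorable missingness.

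**The concern.** With independent residuals of constant variance, which is the PROC MIXED default when nothing else is specified, a participant random intercept is compound symmetry. Every visit has variance σ_b² + σ_e², and every pair of visits has the same correlation. Coding visit as categorical frees the means but not the variances.

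The week-78 contrast then borrows its standard error from all three visits. If the spread of change given baseline is larger at week 78 than earlier, the confidence interval is too narrow and type I error exceeds 5%. If it is smaller, the test is conservative and loses power.

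Growing spread is plausible. Week 78 is 6.5 times as far from baseline as week 12 (78/12), and the protocol describes ApoE4, odor identification and medial temporal volumes as predictors of conversion to AD, which implies that participants decline at different rates. Growth is not established, however, and the documents report no SD of change at any visit.

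Model (1) also serves the neuropsychological composite, UPSA and FAQ. Model (2) and the Hypothesis 4 models keep the same random structure.

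**Working it through.** **The plan's own figure.** Section 4 gives N = 100 for d = 0.58, 80% power, 5% level and 20% dropout. A two-sided two-sample calculation needs 94 without dropout; 94/0.8 rounds up to 118. A longitudinal calculation for week 78 that uses partial data gives power of 75.8% at a within-person correlation of 0.5 and 80.1% at 0.9. So 100 is reachable with a high correlation, but it cannot be confirmed because the correlation is not stated. This does not bear on the point below.

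**Inputs from the SAP.** Visits at weeks 12, 52 and 78; 107 randomized 1:1; dropout uniform to 20% by week 78; 5% level (two-sided assumed).

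**Assumptions.** The SDs of change by visit; and the correlations, either 0.6 throughout or 0.58 (weeks 12-52), 0.70 (52-78) and 0.40 (12-78).

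**Formula with complete data.** Compound symmetry estimates the common variance as the mean of the visit variances, so at week 78

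model SE / true SE = √(mean visit variance / week-78 variance).

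The true level of a nominal 5% test is approximately 2[1 − Φ(1.96 × ratio)].

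For SDs 4, 4.5, 5: mean variance (16 + 20.25 + 25)/3 = 20.42; ratio √(20.42/25) = 0.904; 1.96 × 0.904 = 1.771; level 7.7%.

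**Simulation with dropout.** 4,000 null trials per scenario (Monte Carlo error 0.2-0.5 points), fitting model (1) by REML. Ranges cover both correlation patterns.

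| SDs at weeks 12, 52, 78 | Week 78 vs week 12 | Formula: ratio, level | Simulated ratio | Simulated type I error |
|---|---|---|---|---|
| equal | 0% | 1.00, 5.0% | 0.98-1.00 | 4.9-5.5% |
| 4, 4.2, 4.4 | +10% | 0.96, 6.1% | 0.95-0.96 | 5.9-6.4% |
| 4, 4.5, 5 | +25% | 0.90, 7.7% | 0.90-0.91 | 7.0-7.6% |
| 4, 5, 6 | +50% | 0.84, 9.8% | 0.82 | 10.6% |
| 4, 5.5, 7 | +75% | 0.81, 11.5% | 0.77-0.78 | 12.8-13.2% |
| 5, 4.5, 4 | −20% | 1.13, 2.7% | n/a | 2.0-2.1% |
| 6, 5, 4 | −33% | 1.27, 1.3% | n/a | 1.1-1.3% |

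(n/a: simulated ratio not available.)

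A separate simulation of model (1) at correlation 0.5 agrees: 4.9% with equal SDs, 7.0% for relative SDs 0.8:0.9:1, 11.9% for 0.6:0.8:1 and 2.4% for 1.25:1.1:1.

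**What drives the error.** Unequal variance, not unequal correlation. With equal SDs and correlations of 0.5, 0.4 and 0.7, the SE ratio under 20% dropout is 0.994 (level 5.1%).

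**Alternative fit.** REML with unstructured covariance and Kenward-Roger gave week-78 type I error of 4.0-5.6% in all 14 ADAS-Cog11 scenarios (7 SD patterns by 2 correlations), with no convergence failures. With equal SDs, the mean standard error changed by under 1%.

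**Other outcomes under model (1), week 78.** UPSA (weeks 32 and 78): 7.0-7.6% if the SD is 25% larger at week 78, 9.3-9.8% if 50% larger, 2.7-3.2% if 20% smaller. FAQ (five visits, SD changing linearly): 8.0-9.8%, 11.5-11.7% and 2.2-3.5%.

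**The case against.** No error in this trial's result is shown. Every departure from 5% comes from SD ratios chosen for the calculation, and nothing in the documents supports a week-78 SD 50% or 75% above week 12. That stands: those two rows are stress cases, and the 10% and 25% rows show the effect of moderate growth.

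The arguments for growth are also limited. The protocol's Diagnosis paragraph expected a minority to be diagnosed with dementia, but the SAP reports otherwise: "Since the number of participants transitioning to dementia was very small". COVID delays add little. The protocol says "Total study duration may exceed 78 weeks for those participants encountering delays to in person assessments and/or procedures related to COVID-19" pauses, but it then proposes time in study as a covariate where appropriate, and delays were not confined to week 78. Model (1) contains no such covariate, but that concerns the means rather than the covariance.

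Reading the residual as constant-variance is an inference. It is the natural one for a fit called a random intercept model with nothing further specified. The paper that the SAP supports may give SDs by visit; all that can be said here is that the SAP plans no such table or check.

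Finally, a random intercept with categorical visit is a recognised choice, and the SAP calls this a pilot trial without multiplicity adjustment, so a shift of one to three points on one contrast is modest. This limits the severity but does not remove the point: the exposed contrast is the one that sized the trial, and checking it costs little.

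**Conclusion.** The point holds as a conditional one. Model (1) imposes equal variance across visits. If the spread of ADAS-Cog11 change differs by visit, the week-78 standard error is wrong, and the SAP states no check that would reveal it. The conclusion rests on the default residual structure and on assumed SDs.

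For a week-78 SD 10-25% above week 12, type I error is about 6-8% instead of 5%; for one 20% below, about 2%, with lost power. If the SDs are equal, the analysis is sound whichever of the two correlation patterns holds. The actual direction and size cannot be determined from the documents. This should be fixed, but it is not evidence that the reported result is wrong.

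**What to change.** Refit the same fixed effects in PROC MIXED with REPEATED visit / SUBJECT=id TYPE=UN and DDFM=KR, replacing the random intercept. Three post-baseline visits need 3 × 4 / 2 = 6 covariance parameters. For FAQ, whose five visits need 5 × 6 / 2 = 15, or after non-convergence, use a heterogeneous structure (CSH or TOEPH). Report the SD of change by visit and arm. Keep the week-78 contrast as written.

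The SAP describes completed work: "This statistical analysis plan provides more detailed descriptions of the statistical analyses reported in the paper". Present the refit beside model (1) as a labelled post hoc sensitivity analysis, and qualify the week-78 conclusion if the two disagree.

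The cost is one extra fit per outcome, one table and a few lines of text, with slightly fewer error degrees of freedom. The calibration figures for the unstructured fit are for ADAS-Cog11 only. The FAQ fallback was not simulated, so its convergence and fit should be reported.

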MRI protocol. Image acquisition, pre-processing. At baseline and end-study, subjects at both sites will receive high-resolution T1-weighted IR prepped 3D-SPGR, T2 FLAIR, and GE-EPI resting-state fMRI scans (adapted from ADNI-2, adni.loni.usc.edu). The total scan time is estimated at about 45 minutes. Subjects will receive a clinical read following the MRI scan. While the Table below lists the parameters we plan to obtain, because of software upgrades some of the parameters may change slightly.

WMH assessment. We will rate the severity of WMH on axial T2 FLAIR images using a semi-automated version of the Fazekas modified Coffey Rating Scale which we have used extensively in our studies of cerebrovascular disease. Using our published methods, we derive both total lesion volume as well as volume by ROI that parallels the Fazekas scale. All volume ratings are normalized to adjust for head size using intracranial cross-section area. Our group has shown strong inter-rater reliability ($r > .9$). Both WMH measures will be ancillary and may be included as covariates in analyses because they can influence cognitive ability.

Resting-state fMRI. Acquisition. Resting state: participants will be instructed to remain still with their eyes open and fixated on a white cross-hair displayed on a black background. Following shimming and calibration scans, a single 10-minute resting-state scan will be obtained at baseline and endpoint using the same imaging procedures. Pre-processing. Standard image pre-processing methods will be used with SPM8. Functional images will be assessed for poor quality, though in the proposed study significant loss of data due to this is likely to be small. The data will then be distortion and motion corrected. Non-blood-oxygen- dependent signal variation will be regressed out using time-courses from a region-of interest (ROI) placed in the CSF and in white matter. The resting-state data will then be co-registered with the high-resolution T1- weighted anatomic scan, normalized into the Montreal Neurological Institute (MNI) standard template space and smoothed . We will assess pre- and post-treatment differences in DMN connectivity with a single index for each subject scan (goodness-of-fit GOF index). GOF index is a quantitative measure describing DMN expression in an individual

Protocol Summary Form

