rs-fMRI scan described in our published work and outlined here. Our primary approach will be to analyze the resting-state data time series using group independent components analysis (ICA) as implemented in the Group ICA of fMRI Toolbox. A GOF index that reflects the degree to which DMN maps of subjects with MCI match those of normal controls will be calculated for each subject's scan. We will image all individuals at the last available time-point, including point of dropout. We will control for duration between the two fMRI scans in analyses. We will also use graph theory metrics to compute network parameters in separate analyses.

We will run an exploratory analysis using resting state Spectral Dynamic Causal Modeling (DCM) to determine changes in effective connectivity in specific brain networks as well as more broadly across the whole brain. This Spectral DCM approach will be used to estimate effective connectivity within key networks, on the baseline and post-treatment resting state fMRI scans (N=110, each subject with 2 scans) using SPM12 software. We will first apply DCM to the rsfMRI in the spectral domain (spectral DCM) to estimate a directed network representing effective brain connectivity within the default mode network (DMN). The DMN is a primary *a priori* network of interest for our study based on our prior data from MCI and AD subjects. We will also apply it to the cognitive control network (CCN) and more broadly in an exploratory manner to other networks.

fMRI:

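### Neither SAP model for MRI change includes the scan interval or says which follow-up scans enter, although the protocol plans scans at dropout and expects late scans

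*SAP*

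**What the plan says.** **SAP.** Section 3 defines the exploratory outcomes as "change in hippocampal volume from baseline to 78 weeks" and the corresponding change in cortical thickness. The hypothesis is less decline with Games. Section 5 fits a linear regression to "compare the effect of treatment on change in MRI outcome (baseline minus 78 weeks), adjusting for baseline values of the MRI measure", and a second version adds the randomisation strata (site, age group, MCI type). Scan interval appears in neither version. The SAP gives no visit window for the second scan, no rule for scans taken early or late, and no weighting for missing scans.

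**Protocol.** Four places bear on this.

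- Resting-state fMRI text under Assessment Instruments: "We will image all individuals at the last available time-point, including point of dropout". The next sentence reads: "We will control for duration between the two fMRI scans in analyses".
- MRI protocol paragraph in the same section: "At baseline and end-study, subjects at both sites will receive high-resolution T1-weighted IR prepped 3D-SPGR, T2 FLAIR, and GE-EPI resting-state fMRI scans". The structural and functional images are thus planned for the same time points.
- Study duration paragraph under Study Procedures: "Total study duration may exceed 78 weeks for those participants encountering delays to in person assessments and/or procedures related to COVID-19 specific pauses". Time in study is to be considered as a covariate for outcome measures where appropriate.
- Paragraph on intent to treat, dropouts and missing data: for MRI outcomes with one pre and one post measure, complete cases are to be weighted by inverse probability, with weights based on the probability of completing rather than dropping out.

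**The concern.** Hippocampal volume and cortical thickness are analysed as quantities that decline, and a decline that accrues over time depends on how long one waits between scans. Change is coded as baseline minus follow-up, so a scan taken at an early exit shows less loss than the same person would have shown at week 78. A scan delayed by the pandemic shows more.

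The protocol foresaw both situations and named remedies. The SAP carries none of them into the MRI model: no scan interval, no time in study, no weighting. If off-schedule scans are in the analysis, the spread of intervals goes into the residual. If the mean interval also differs between arms, the difference enters the treatment estimate, and the arm with the shorter intervals appears to decline less, which is the quantity the hypothesis tests.

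**Working it through.** The plan states no figure for this analysis, so there is nothing to reproduce. The check compares the texts and then asks how large the effect could be.

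**Text comparison**

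| Item | Protocol | SAP MRI model |
|---|---|---|
| Second scan before week 78 | planned at dropout | not mentioned |
| Second scan after week 78 | possible through COVID-19 pauses | not mentioned |
| Scan interval | to be controlled (worded for fMRI) | absent from both models |
| Time in study | to be considered where appropriate | absent |
| Missing second scan | inverse probability weighting of completers | absent |

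**Inputs for size**

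- Planned dropout: 20% by week 78, uniform over time (SAP Section 4).
- Completion: 95 of 109 enrolled (protocol progress summary).
- Randomised: 107 (SAP Section 2).
- Assumptions not in the documents: linear loss over time, every dropout scanned on leaving, and the split of dropout between arms.

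**Mean interval.** With a fraction d dropping out uniformly over 78 weeks, the mean exit time is week 39, so

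mean interval = 78(1 − d) + 39d = 78 − 39d.

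- d = 20%: 78 − 7.8 = 70.2 weeks, 10% short of 78.
- d = 14/109 = 12.8%: 78 − 5.0 = 73.0 weeks, 6.4% short.

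**Bias between arms.** Under linear loss and no treatment effect, the bias as a fraction of the 78-week change is the difference in mean interval divided by 78, which equals (d₁ − d₀)/2. Each week of difference is worth 1/78 = 1.3% of the 78-week change, whether it comes from early or late scans.

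| Dropout by arm (assumed) | Mean intervals, weeks | Bias, share of 78-week change |
|---|---|---|
| 20% and 20% | 70.2 and 70.2 | 0 |
| 15% and 25% | 72.15 and 68.25 | 5% |
| 10% and 30% | 74.1 and 66.3 | 10% |

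**Effect on the test.** A simulation of 107 participants (4,000 runs, no treatment effect) regressed change on group, with and without interval. The documents give no atrophy rate, so the ratio of mean 78-week change to its SD was varied. Results for 10% versus 30% dropout:

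| Mean/SD of 78-week change (assumed) | Bias without interval, SD | Type I error without interval |
|---|---|---|
| 0.5 | 0.05 | 6.1% |
| 1.0 | 0.10 | 7.6% |
| 1.5 | 0.15 | 10.7% |
| 2.0 | 0.20 | 16.0% |

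For scale, the standard error of the arm difference is about √(1/53 + 1/54) = 0.19 SD. With 20% dropout in both arms, bias was about zero and type I error 4.6% to 5.3%. With interval in the model, bias was at most 0.004 SD and type I error 4.4% to 5.2% in every scenario. Restricting to week-78 scans also gave bias near zero. In the simulation, dropout was unrelated to outcome within arm, so it does not test selection.

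**How extreme is 10% versus 30%?** It implies 0.10 × 53 + 0.30 × 54 = 21.5 exits. If all 95 completers were among the 107 randomised, there were 12 non-completers. A gap of 20 percentage points needs about 0.20 × 53.5 = 10.7 more exits in one arm, so nearly all 12. The 10% row is therefore towards the upper end for dropout alone.

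**The case against.** Several arguments limit the point, and most of them stand.

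- **The protocol's interval commitment is for fMRI, and the SAP outcomes are structural.** A reader might infer that the SAP breaks a stated commitment for hippocampal volume and cortical thickness. The text does not support that. The link is that both sequences are planned for the same time points, plus the general wording on time in study, which applies only where appropriate. This makes an interval term sensible, not owed.
- **The SAP may have used week-78 scans only.** A reader might infer that every MRI change is treated as a 78-week change and that exit scans look like less atrophy. The SAP does not say which scans entered. The protocol's weighting of completers suggests that dropouts might be left out. In that case the short-interval mechanism does not arise for them, and the gap is an unweighted completer analysis. Late scans would remain an open question.
- **The models adjust for more than baseline.** This is true: the second version adds the three strata. None of them stands in for scan interval.
- **Few exit scans may exist.** The listed reasons for leaving include death, long hospitalisation and unwillingness to return in person. The progress summary for the New York site mentions one early exit with all endpoint measures done and one loss to follow-up.
- **Pandemic delays are driven by calendar time.** Randomisation should balance them in expectation. The SAP also compares COVID-19 treatment interruption by arm, although that is not scan timing.
- **Interval arises after randomisation.** It could depend on treatment through dropout, so adjusting for it is not free of assumptions.

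None of this removes the basic gap: the protocol allows for unequal intervals in an outcome expected to change with time, and the SAP neither excludes off-schedule scans nor accounts for their timing.

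**Conclusion.** The point holds as an omission in the MRI model and in the rule for selecting scans. It does not show that the reported MRI comparison is biased. If off-schedule scans were analysed, unequal intervals add variance that could have been removed. They distort the arm comparison only to the extent that mean intervals differ by arm, and no document shows that they do.

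The actual size is unknown. Under linear loss with every dropout scanned, the illustrations run from about zero (equal dropout) to about 10% of the 78-week change (10% versus 30%), in favour of the arm with more exits. Late scans push the other way. The outcome is exploratory and the SAP calls the trial a pilot, so this is a minor improvement and does not touch the primary analysis.

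**What to change.** In SAP Section 5, under the exploratory hypothesis:

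1. State which follow-up scans enter. Include exit and late scans with their actual interval.
2. Add the baseline-to-follow-up scan interval in weeks, centred at 78, to both MRI regressions.
3. Report the interval by arm, with the number of scans before and after the week-78 visit.
4. Show the result without the interval term alongside, because the interval is a post-randomisation variable.
5. As a sensitivity analysis, give the week-78 completers with the inverse probability weighting the protocol planned.

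The cost is one degree of freedom per model, a short table built from the scan dates, one extra analysis and a few sentences of SAP text. No new data collection is needed.

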# 2. Study Design

One hundred and seven participants aged 55-95 years with clinical diagnosis of MCI were randomized to Games or Crosswords at 1:1 ratio. The randomization was stratified by site (Columbia or Duke), MCI type (early or late MCI), and age (70 years and below or 71 and above). Block randomization of random size (2,4) was used to prevent clinicians from guessing what the next participant's treatment might be. Participants were evaluated at five scheduled visits (Weeks 0, 12, 32, 52, and 78) and research staff conducted three scheduled phone calls (Weeks 20, 42, and 64). Home-based computerized training for Games or Crosswords comprised four 30-minute training sessions weekly for 12 weeks. The six booster sessions each consisted of four 30-minute sessions. At weeks 32, 52, and 78, participants completed three booster sessions at home and the fourth in-clinic. At weeks 20, 42, and 64, participants completed all four booster sessions at home.

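### The exploratory MRI regressions are fitted in PROC GENMOD with no scale estimator or t/F reference stated; under default settings their 5% tests would run at about 5.6–6.3%

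*SAP*

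**What the plan says.** SAP section 3 lists two exploratory MRI outcomes: "change in hippocampal volume from baseline to 78 weeks; change in cortical thickness from baseline to 78 weeks". Section 5 analyses each by linear regression of the change on treatment, "adjusting for baseline values of the MRI measure". A second model follows: "The model was then further adjusted for the three stratification variables". Section 2 gives those variables as two-level factors; randomization was "stratified by site (Columbia or Duke), MCI type (early or late MCI), and age (70 years and below or 71 and above").

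On estimation, the MRI paragraph says: "Parameters were estimated using SAS PROC GENMOD procedure with normal distribution and identity link". It names no scale option, type of test (Wald, likelihood ratio or F), reference distribution, weights or robust variance. For the longitudinal cognitive and functional outcomes, by contrast, "SAS PROC MIXED procedure was used to estimate the parameters using REML".

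Two general statements also apply: "All hypotheses were tested at level of significance of 5" per cent, and "All analyses were conducted using SAS 9.4". Section 5 makes no multiplicity adjustment.

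The protocol paragraph on intent to treat, dropouts and missing data (under Study Procedures) plans inverse probability weighting of complete cases for MRI outcomes. The SAP's MRI paragraph does not mention it.

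**The concern.** A single pre/post change regressed on a few covariates is an ordinary linear model, for which exact t-based inference is available. A generalized linear model routine fitted by maximum likelihood can depart from that in two ways. The residual variance can be the residual sum of squares (RSS) divided by n rather than by n minus the number of mean parameters p. The group coefficient can be referred to the normal rather than the t distribution. Both narrow the intervals and lower the p-values, and neither gains anything. The variance shortfall grows with p, so it is larger once the stratification variables enter.

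The MRI p-values and intervals are at stake. There are two outcomes and two models each, so four group tests, each judged at an unadjusted 5%.

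**Working it through.** The 5% is a chosen nominal level, so there is no plan calculation to reproduce. The check is what level the described analysis attains.

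**Inputs**
- Level: 5% (SAP section 5). Sidedness is not stated; two-sided is assumed.
- First model: p = 3 (intercept, group, baseline MRI value).
- Second model: p = 3 + 3 = 6, since three two-level factors add one parameter each.
- n with both scans: not given. The ceiling is 107 randomized (SAP section 2). The protocol's progress summary reports 95 study completers. The 20% dropout planned in SAP section 4 gives 0.8 × 107 = 85.6, or 0.8 × 100 = 80 on the original sample size. The range used is 80–107.
- Assumed settings: scale estimated by maximum likelihood, Wald test and interval with a normal reference, no weights, no robust variance, normal errors.

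**Formulas**
- Standard error relative to the correct one: sqrt((n − p)/n).
- True level: 2 × P(t with n − p df > 1.96 × sqrt((n − p)/n)).
- Coverage: 1 minus the true level.
- Interval width relative to the correct one: 1.96 × sqrt((n − p)/n) / t(0.975, n − p).

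For n = 80, p = 6, the standard error ratio is sqrt(74/80) = 0.9618. The effective critical value is 1.96 × 0.9618 = 1.885, and the two-sided tail of t with 74 df beyond it is 0.0634.

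| n | p | SE ratio | True level | Coverage | Width ratio |
|---|---|---|---|---|---|
| 107 | 3 | 0.9859 | 5.60% | 94.40% | 0.9744 |
| 95 | 3 | 0.9841 | 5.68% | 94.32% | 0.9711 |
| 85 | 3 | 0.9822 | 5.77% | 94.23% | 0.9677 |
| 80 | 3 | 0.9811 | 5.82% | 94.18% | 0.9657 |
| 107 | 6 | 0.9716 | 5.97% | 94.03% | 0.9599 |
| 95 | 6 | 0.9679 | 6.11% | 93.89% | 0.9547 |
| 85 | 6 | 0.9641 | 6.25% | 93.75% | 0.9493 |
| 80 | 6 | 0.9618 | 6.34% | 93.66% | 0.9460 |

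Standard errors are thus 1.4–1.9% too small with 3 parameters and 2.8–3.8% too small with 6. Intervals are 2.6–3.4% and 4.0–5.4% too narrow.

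**Simulation check** (200,000 replicates each): 5.82% (n = 80, p = 3), 6.30% (80, 6), 5.72% (95, 3) and 6.06% (95, 6), in agreement with the formula.

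**Other settings, same range of n**
- Likelihood-ratio chi-square test, level P(n × log(1 + t²/(n − p)) > 3.841): 5.4–5.5% (p = 3) and 5.8–6.0% (p = 6).
- Unbiased scale, RSS/(n − p), with a normal reference: 5.3–5.4%.
- Unbiased scale with a t or F reference: exactly 5.0%, with 95.0% coverage.

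**The case against.** The strongest objection is that the premise is not in the documents. The SAP names the procedure, distribution and link and nothing more; the maximum-likelihood scale and normal reference are inferred from how the software behaves when no option is given. With a t or F reference and the unbiased scale there is no error at all. This stands, and the finding has to be conditional. The documents do not rule the defaults out either, and every alternative computed above other than a t or F reference still exceeds 5%.

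A reader might infer that the MRI tests simply run at 6–6.5%. The documents do not support that. The first-listed, baseline-adjusted model stays below 6% throughout the range. A level near 6.5% needs the 6-parameter model with n close to 70 (6.55% there), and no figure in either document points to so few scans.

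A reader might also infer that adding the strata could make a result look markedly more significant. At n = 95 the extra artificial shrinkage is 0.9841/0.9679 = 1.017, which moves a z of 1.90 to about 1.93.

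The planned inverse probability weighting is a further limit. If weights or robust errors were used, these figures do not apply directly. The SAP neither repeats nor withdraws that plan.

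Finally, the MRI hypothesis is exploratory, in a self-described pilot with no multiplicity control, so an excess of about 0.6–1.3 points is minor. That is fair as to importance. It does not justify an approximation when the exact analysis of the same model is readily available.

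**Conclusion.** The concern holds as a small, conditional error. If GENMOD defaults were used without weights or robust errors, the tests run at about 5.6–5.8% (baseline-adjusted) and 6.0–6.3% (strata-adjusted) instead of 5%, for an assumed 80–107 participants with both scans. Coverage is about 94.2–94.4% and 93.7–94.0%.

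In practice, a conclusion changes only for a result whose correct p-value lies between 0.05 and the true level: for example, between 0.050 and 0.061 for the adjusted model at n = 95. The primary ADAS-Cog analysis, fitted by REML in PROC MIXED, is not affected, and Hypotheses 1 to 4 do not use this procedure.

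The conclusion rests on the default settings, two-sided testing, normal errors and the assumed n.

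**What to change.** Refit the same MRI models with the unbiased residual variance and t-based tests and intervals, using PROC GLM or PROC REG, or PROC MIXED with REML. Update the reported MRI p-values and intervals, and revise the GENMOD sentence in SAP section 5 to match. Because the SAP describes analyses already carried out, changing the sentence without rerunning the models would misdescribe what was done. If the options actually used already gave the unbiased variance and a t or F reference, it is enough to state them.

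Report the number of participants with both scans, and say whether the protocol's inverse probability weighting was applied. If it is, use the weights with a suitable robust, small-sample-corrected variance rather than the unweighted refit.

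The cost is two outcomes by two models to rerun and a small text change. Relative to the default Wald intervals, the correct ones are wider by about 2.6–3.6% (1/0.9744 to 1/0.9657) in the first model and 4.2–5.7% (1/0.9599 to 1/0.9460) in the second.
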